## 4.3. Risk-Benefit Assessment

Two studies were recently completed to support dasotraline as a safe and efficacious treatment for adults with ADHD with minimal abuse potential.

The first study, SEP360-201, a randomized, double-blind, parallel-group, outpatient study at 30 sites, evaluated the efficacy and safety of dasotraline in adults with ADHD using 2 doses (4 mg/day or 8 mg/day) versus placebo over a 4-week treatment period. In this study, clinically meaningful treatment effects were observed for both dasotraline 4 mg/day and 8 mg/day compared to placebo. For the primary efficacy endpoint, change from baseline in ADHD RS-IV with adult prompts total score at week 4, statistical significance was achieved for dasotraline 8 mg/day compared to placebo (adjusted p = 0.019) with a strong trend for dasotraline 4 mg/day (adjusted p = 0.076). Efficacy with both doses was observed for the secondary endpoint change from baseline in CGI-S (4 mg group p = 0.021; 8 mg group p = 0.013). A dose response relationship was observed supporting pharmacological activity in ADHD. Decreases in 3, 4-dihydroxyphenylglycol (DHPG) concentrations indicated the presence of central NET inhibition. Treatment-emergent AEs (TEAEs) were consistent with dasotraline pharmacology, ie, insomnia, decreased appetite, dry mouth, and headache. Worsening of insomnia associated with

dasotraline was characterized by TEAEs, and shifts in Insomnia Severity Index (ISI) total score, particularly with dasotraline 8 mg/day. TEAEs, particularly insomnia, were the most frequent reason for discontinuation of dasotraline 8 mg/day. Decreases in mean body weight were generally greater for dasotraline 8 mg/day than 4 mg/day. Increases in mean supine and standing heart rate observed during treatment and follow-up were generally higher on dasotraline 8 mg/day than 4 mg/day.

No signs or symptoms of withdrawal upon discontinuation of dasotraline were observed for either dose. In addition, there was no evidence of drug liking or deterioration of psychiatric symptoms associated with either dose of dasotraline. No misuse or diversion of dasotraline was detected through the abuse potential monitoring plan

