## 10. TREATMENT OF SUBJECTS

## 10.1. Study Medication

Dasotraline 2, 4, and 6 mg capsules for oral administration will be supplied for the study as described in Section 9.1.

Under supervision from the subject's parent/legal guardian, subjects will self-administer the study drug on an outpatient basis beginning on Day 1, the morning following the OL Baseline visit. All dasotraline doses will consist of 1 capsule taken orally once a day for 26 weeks (Day 1 through Day 182) at approximately the same time each morning including on the days when clinic visits occur. If morning dosing is not tolerated then dosing may be at another time of day with prior medical monitor approval; however, if there is a time of day dosing change, subjects should administer study drug at the same time of day for the remainder of the study.

Subjects may take study drug with or without food.

Study drug capsules should not be opened or tampered with in any way; the active ingredient is an ocular irritant.

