# 12.3. Collection and Recording Adverse Events

All AEs must be collected and recorded in the subject's study records/source documents, in accordance with the Investigator's normal clinical practice, and on the CRF from the time the informed consent/assent is signed through the last study visit or discontinuation. All AEs will be followed up until resolution, stabilization of the condition, the event is otherwise explained, or the subject is lost to follow-up.

Each AE is to be evaluated for duration, severity, frequency, seriousness, action taken with the study treatment, outcome, and causal relationship to the study treatment. Definitions for severity, frequency, action taken with the study treatment, outcome, and causal relationship to the study treatment are presented below.

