12.1. ADVERSE EVENTS (AEs)

The summary of AEs (or SAEs) will be limited to TEAEs. A TEAE is any AE (or SAE) occurring on or after the date of the first dose of study drug in the SEP360-310 study. All AEs will be coded using MedDRA version 19.0.

TEAEs will be further divided into:

- 1.) Those events with onset between the date of the first dose of study drug in the SEP360-310 study and 3 days after the last dose of study medication in SEP360-310, inclusive. These will be called on treatment events.
- 2.) Those events with onset more than 3 days after the last dose of study medication in SEP360-310. These will be called post-treatment events.

AEs with preferred terms of “Insomnia”, “Initial insomnia”, “Middle insomnia”, or “Terminal insomnia”, or AEs with Higher Level Term of “Disturbances in initiating and maintaining sleep” will be presented on AE tables in a combined term called “Combined insomnia” with the individual preferred terms within the combined term directly underneath.

All TEAEs will be summarized by SOC and PT. Though only TEAEs will be included in the summary tables, all AEs will be included on the listings (non-TEAEs will be flagged).

An overall summary table of TEAEs by DB treatment will be produced for the following categories:

- Number and percentage of subjects with a TEAE
- Number and percentage of subjects with a treatment-related TEAE
- Number and percentage of subjects with a TEAE leading to discontinuation
- Number and percentage of subjects with a Treatment-related TEAE leading to discontinuation
- Number and percentage of subjects with a serious TEAE
- Number and percentage of subjects with a serious TEAE leading to discontinuation
- Number and percentage of subjects with a treatment-related serious TEAE
- Number and percentage of subjects with a Treatment-related serious TEAE leading to discontinuation
- Number and percentage of subjects with a TEAE leading to death

This overall summary will be repeated for each onset period. For the post-treatment events, the denominators will be the number of subjects in each DB treatment group whose end of study visit was more than 3 days after the last dose date.

Subgroup analyses of the above noted TEAE categories will be produced for the following subgroups (sex, race (categorized as White, Black or African American, Asian, and Other), DB baseline age group (6-9 vs. 10-12 years)).

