Adverse events will be summarized by DB treatment and overall for subjects in the safety population. The following summaries of AEs will be provided:

- TEAEs by SOC and PT
- TEAEs by PT
- TEAEs by PT ($\geq 3\%$ in any DB treatment group)
- Serious TEAEs by SOC and PT
- TEAEs leading to discontinuation by SOC and PT
- TEAEs by SOC and PT and maximum severity. Missing severity, if any, will be assumed as 'severe'.

- TEAE by relationship to study treatment (related or not related) by SOC and PT. Missing relationships, if any, will be assumed to be ‘related’.
- Treatment related SAEs by SOC and PT

The prevalence of Insomnia by study day in the study will be presented graphically by DB treatment and overall. Combined insomnia events will be used for this analysis. On any study day, the numerator will be the number of subjects who were experiencing insomnia (noting that subjects may have experienced multiple episodes during the study), and the denominator will be the number of subjects remaining on open-label study drug treatment.

The following listings of AEs will be provided:

- All AEs
- Adverse events leading to discontinuation of study drug
- Serious adverse events

In the summary tables subjects may be counted under multiple SOC and PTs, but for each SOC and PT, subjects are only counted once. If a subject has the same AE on multiple occasions, the highest severity (severe, moderate, mild) recorded for the event will be presented and the highest drug relationship (1 = ‘Unrelated’, 2 = ‘Unlikely to be Related’, 3 = ‘Possibly Related’, 4 = ‘Probably Related’, 5 = ‘Related’), reclassified into Related (‘Possibly Related’, ‘Probably Related’, ‘Related’) or Not Related (‘Unrelated’ and ‘Unlikely to be Related’), will be presented on the respective tables. Percentages are based on the number of subjects in the safety population.

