12.7. NEUROLOGICAL EXAMINATION

Neurological examinations will be performed at Open-Label Baseline, Week 14, Week 26 or ET, and End of Study.

Each assessment (i.e. Cranial Nerves, Motor System, Sensory System, Reflexes, Coordination, Gait and Romberg's test) will be summarized using summary statistics for categorical variables (normal/abnormal) at each visit by treatment and overall. All percentages will be based on the number of safety subjects in each DB treatment group.

Shift table for baseline condition vs. the worst result during the treatment period (Abnormal > Normal) will be produced by DB treatment and overall. Percentages will be based on the number of subjects in the safety population. The number of subjects without an assessment at the visit will be noted on the shift table.

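### Three descriptive safety displays (insomnia by day, neurological examination, Tanner stage) need a small correction to how their percentages are defined; primary adverse-event incidence is unaffected

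*SAP*

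**What the plan says.** **Insomnia plot.** SAP 12.1 says: "The prevalence of Insomnia by study day in the study will be presented graphically by DB treatment and overall". Combined insomnia events are used. On each study day "the numerator will be the number of subjects who were experiencing insomnia", and "the denominator will be the number of subjects remaining on open-label study drug treatment". Only the denominator is tied to being on drug. The same section counts any event from the first open-label dose onward as treatment-emergent, with no upper time limit. Events starting more than 3 days after the last dose are labelled post-treatment. For the overall summary of those events it does set a matching base, limited to children whose final visit fell beyond that 3-day margin.

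**Neurological examination.** SAP 12.7 reports each component as normal or abnormal at each visit, and "All percentages will be based on the number of safety subjects in each DB treatment group". The shift from baseline to worst result also uses the whole safety population, and the number without an assessment is to be noted on that shift table. SAP Appendix 2 (18.2.5.1) gives subjects assessed as the normal base, then allows that many cases need thought and that the base is usually the number exposed. SAP 6.1 and the shift tables in SAP 12.2 and 12.8 use subjects with both a baseline and a post-baseline value.

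**Tanner stage.** SAP 12.11 collects the stage at OL Baseline and at Week 26 or Early Termination, and defines the shift between those two. It then bases the percentages on subjects assessed at baseline and EOS. EOS is Visit 13E (Week 29). Neither Protocol Table 2, Protocol 11.4.11.3 nor SAP Appendix 1 schedules Tanner staging at that visit.

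**The concern.** A prevalence needs a numerator drawn from its own denominator. For insomnia the SAP text does not secure this, and the data that would break it will be collected. Protocol 12.3 says: "All AEs will be followed up until resolution, stabilization of the condition, the event is otherwise explained, or the subject is lost to follow-up". Protocol 13.1 asks children who stop early to complete the termination visit, the withdrawal calls and the EOS visit. A child who stops drug with insomnia continuing therefore leaves the denominator but, on the literal text, stays in the numerator. Insomnia is also the event most likely to be examined: in the adult study, "TEAEs, particularly insomnia, were the most frequent reason for discontinuation of dasotraline 8 mg/day" (Protocol 4.3).

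The neurological rule is internally coherent, but it mixes two quantities, how often the examination is abnormal and how many children were examined. A constant abnormal rate would look like a decline as children leave. Taken at its word, the Tanner rule would leave almost every subject out of the base for a listed secondary evaluation.

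**Working it through.** The plan states no figure to reproduce. The study is descriptive, the documents give no dropout or event rates, and 330 is a projected maximum (SAP 4.2). Every rate below is an assumption, used only to show scale.

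**(a) Insomnia.** On a given day let n be the number on drug, k the number of those with insomnia, and x the number off drug with insomnia.

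- Literal rule: (k + x)/n. On-drug prevalence: k/n. Excess: x/n, so each off-drug child adds 1/n.
- With n = 250: 1/250 = 0.40 points.
- One double-blind group, assuming 330 subjects in equal thirds and 35% dropping out evenly over 182 days. At Day 120, n = 110 × (1 − 0.35 × 120/182) = 84.6, and 1/84.6 = 1.18 points (1.05 at 20% dropout, 1.36 at 50%).
- End of treatment. Planned dosing ends on Day 182 (Protocol 10.1), but the Week 26 visit window is ± 3 days (Protocol Table 2). Completers: 330 × 0.65 = 214.5. If last doses spread evenly over Days 179 to 185, then 214.5/7 = 30.6 are on drug on Day 185, and 1/30.6 = 3.3 points (2.7 at 20% dropout, 4.2 at 50%). After that n = 0 and the ratio is undefined.
- Instability, with 5% of on-drug children affected and x = 5: n = 300 gives 20/300 = 6.7%; n = 100 gives 10/100 = 10.0%; n = 20 gives 6/20 = 30.0%. On-drug prevalence is 5.0% each time. With n = 5 and k = 1 the literal value is 6/5 = 120%.

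The total excess depends on x. That in turn depends on how many children get insomnia, how many of them stop drug, and how long it lasts afterwards. The documents give none of these, so no total is offered.

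**(b) Neurological examination.** Reported percentage = (rate among those examined) × (share examined). Assume a constant 5% abnormal and even dropout d over 182 days.

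- No termination examinations counted: Week 14 share = 1 − d × 98/182; Week 26 share = 1 − d.
- All termination examinations done and remapped under SAP 6.2.4: add d × 25/182 to each (termination on Days 74–98 and 158–182).

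| Dropout | Week 14 shows | Week 26 shows |
|---|---|---|
| 20% | 4.46 to 4.60% | 4.00 to 4.14% |
| 35% | 4.06 to 4.30% | 3.25 to 3.49% |
| 50% | 3.65 to 4.00% | 2.50 to 2.84% |

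At 35% dropout the shares are 0.812 to 0.860 at Week 14 and 0.650 to 0.698 at Week 26. The normal percentage shrinks by the same factor, so the assessed rate can be recovered: with 65% examined, abnormal 3.25% and normal 61.75% give 3.25/65.00 = 5%. No fall is claimed at EOS, because early stoppers are also asked to attend that visit. Dilution is weaker in the shift table, where a termination examination can supply the post-baseline result.

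**(c) Tanner stage.** The shift is defined to Week 26 or Early Termination, the base to EOS, and no staging is scheduled at EOS. The only route to an EOS-labelled stage is SAP 6.2.4, which relabels a termination visit held more than 3 days after the last dose as EOS when the EOS visit is missing. The literal base is otherwise empty.

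**The case against.** On insomnia, the two halves of the rule stand in one sentence, and the ordinary reading of a prevalence among children on drug makes the numerator a subset. The figure shells are a separate attachment and may say so. Any error overstates harm, so it cannot hide a signal, and tabulated insomnia incidence uses the safety population. All of this is fair. What remains is that the SAP text leaves the condition unstated, although the same section does spell out a matching base for post-treatment events.

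On the neurological table, the base is openly stated, Appendix 2 allows exceptions, the assessed rate can be recovered from the counts, and clinically significant findings are also recorded as adverse events (Protocol 11.3.3). A reader might infer a contradiction with SAP 6.1. The documents do not support that: 6.1 is worded per visit, while this shift uses the worst result. The point is one of consistency with the usual convention and with the other shift tables. It still has practical weight, because the count not assessed is promised only for the shift table and not for the by-visit table, where dilution is clearest.

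On Tanner stage, the preceding sentence and SAP 6.1 already show the intended base. That objection stands in full, and only a wording correction is left.

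**Conclusion.** The point holds as a minor, descriptive correction. The insomnia numerator needs an explicit on-drug condition. The neurological base makes percentages at Weeks 14 and 26 depend on attrition. The Tanner base names the wrong visit.

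Three stronger inferences are not supported. First, primary adverse-event incidence is not affected, because SAP 12.1 bases it on the safety population. Second, the insomnia curve cannot be said to be inflated by any particular amount: only the per-child effect can be calculated, that effect rests on assumed enrolment split and dropout, and the excess is zero if no off-drug child has insomnia. Third, the neurological rule does not conceal abnormal findings; it dilutes percentages whose counts remain visible. The neurological sizes rest on the assumed 5% rate and even dropout.

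**What to change.** - **SAP 12.1:** count in the numerator only subjects on open-label drug that study day, show the number on drug under the axis, and plot only days with subjects on drug. A fixed stop at Day 182 is not advised, because the Week 26 window runs to Day 185 and on-drug days would be lost.
- **SAP 12.7:** base by-visit percentages on subjects assessed at that visit and shift percentages on subjects with both a baseline and a post-baseline result. Keep the count not assessed.
- **SAP 12.11:** in the percentage base, replace EOS with Week 26 or Early Termination.

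The cost is a few SAP sentences and minor programming. Protocol 15.3.6.5 and 15.3.6.6 set no percentage base, so those sections need no change. The insomnia curve becomes equal or lower. The downside is that neurological abnormal percentages become slightly less favourable.

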12.2. LABORATORY EVALUATIONS

The following laboratory tests are planned to be performed:

HEMATOLOGY: (Differential reported as % and absolute value)

Hemoglobin, Hematocrit, Platelet Count, red blood cell (RBC) count, white blood cell (WBC) - total count, WBC differential reported as % and absolute values to include basophils, eosinophils, lymphocytes, monocytes, neutrophils.

BLOOD CHEMISTRIES:

Alanine aminotransferase (ALT), Alkaline Phosphatase (ALP), Aspartate aminotransferase (AST), Bicarbonate (HCO₃), Bilirubin (Total, Direct, Indirect), Blood Urea Nitrogen (BUN), Calcium (Ca), Chloride (Cl), Creatinine, Glucose, Magnesium

(Mg), Phosphorus (P), Potassium (K), Protein (Total), Sodium (Na), Uric Acid, Albumin

URINALYSIS:

Blood, Glucose, Ketones, Leukocyte Esterase, Microscopic Examination, Nitrites, pH, Protein

THYROID PANEL:

Free T3, Free T4, Thyroid stimulating hormone (TSH)

LIPID PANEL:

LDL-Cholesterol, HDL-Cholesterol, Total Cholesterol, Triglycerides

SEX HORMONES:

For females: estradiol, follicle-stimulating hormone (FSH), and luteinizing hormone (LH).

For males: testosterone.

URINE DRUG SCREENING:

Amphetamines, Barbiturates, Benzodiazepines, Cannabinoids, Cocaine, Methamphetamines, Methadone, Methylenedioxymethamphetamine (MDMA), Phencyclidine (PCP), Opiates, Oxycodone, Tricyclic Antidepressants

OTHER TESTS:

Breath Alcohol Test, Serum Pregnancy (B-hCG) (in female subjects only), Urine Pregnancy Test (in female subjects only)

Hematology, chemistry, urinalysis, thyroid panel, lipid panel, and sex hormones are collected at Open-label baseline, Week 14, Week 26 or ET, and the EOS Visit.

The laboratory results collected in conventional units will be converted to SI units, and the SI units will be used for all of the summaries and listings. Clinical laboratory test results (hematology, chemistry, urinalysis, thyroid panel, lipid panel, and sex hormones) and their changes from DB baseline and OL baseline will be summarized by DB treatment and overall, and by visits including the endpoint (Week 26 LOCF), using descriptive statistics. For hematology, chemistry lipid panel, thyroid panel, and sex hormone tests, result will also be categorized as “Normal”, “Low”, or “High” based on their normal ranges. For urinalysis results, tests will be classified as “Normal” or “Abnormal”. Shift tables comparing laboratory test results from baseline to Week 26

LOCF will be presented. Percentages are based on the number of the safety subjects in a high, low or normal category with non-missing values for both baseline and post-baseline at the given visit.

In addition, the markedly abnormal post-baseline laboratory results will be summarized for certain laboratory tests.

Summaries will be presented separately for hematology and chemistry for subjects with at least one markedly abnormal value during the open-label treatment period. A listing of all markedly abnormal results will be provided.

The criteria for markedly abnormal values are defined below.

Parameter (Unit)	Markedly Abnormal Range (Conventional Unit)	Conversion Factor (Conventional to SI) / SI unit	SI Unit Markedly Abnormal Range
Hematology			
Hemoglobin (g/dL)	Female: ≤ 9.5, Male: ≤ 11.5 ≥ 17.2	10 / g/L	Female: ≤ 95 g/L, Male: ≤ 115 g/L, ≥ 172 g/L
Hematocrit (fraction, %)	≤ 30, ≥ 50	0.01 / (fraction of 1)	≤ 0.30, ≥ 0.50 (1)
WBC (10 ³ /μL)	≤ 2.8, ≥ 16	1 / x10 ⁹ /L (PPD Conv unit K/cu mm)	≤ 2.8, ≥ 16
RBC (10 ⁶ /μL)	≤ 3.0, ≥ 6.0	1 / x10 ¹² /L (PPD Conv unit x10 ⁶ /cu mm)	≤ 3.0, ≥ 6.0
Platelet Count (10 ³ /μL)	≤ 100, ≥ 500	1 / x10 ⁹ /L (PPD Conv unit K/cu mm)	≤ 100, ≥ 500
Eosinophils (%)	≥ 10	1 / %	≥ 10

Parameter (Unit)	Markedly Abnormal Range (Conventional Unit)	Conversion Factor (Conventional to SI) / SI unit	SI Unit Markedly Abnormal Range
Neutrophils (%)	≤ 15	1 / %	≤ 15
Clinical Chemistry			
ALP (U/L)	≥ 3 x ULN	1 / U/L	≥ 3 x ULN
ALT (U/L)	≥ 2 x ULN	1 / U/L	≥ 2 x ULN
AST (U/L)	≥ 2 x ULN	1 / U/L	≥ 2 x ULN
Total Bilirubin (mg/dL)	≥ 2.0	17.1 / μmol/L	≥ 34.2
Albumin (g/dL)	< 50% LLN	10 / g/L	< 50% LLN
Creatinine (mg/dL)	≥ 2.0	88.4 / μmol/L	≥ 176
Creatine Phosphokinase (CPK) (U/L)	≥ 450	1 / U/L	≥ 450
LDH (U/L)	≥ 3 x ULN	1 / U/L	≥ 3 x ULN
GGT (U/L)	≥ 150	1 / U/L	≥ 150
Sodium (mEq/L)	≤ 130, ≥ 150	1 / mmol/L	≤ 130, ≥ 150
Potassium (mEq/L)	≤ 3, ≥ 5.5	1 / mmol/L	≤ 3, ≥ 5.5
Bicarbonate (mEq/L)	< 18, > 30	1 / mmol/L	< 18, > 30
Calcium (mg/dL)	< 8.4, or > 11.5	0.25 / mmol/L	< 2.1, or > 2.8

Parameter (Unit)	Markedly Abnormal Range (Conventional Unit)	Conversion Factor (Conventional to SI) / SI unit	SI Unit Markedly Abnormal Range
Chloride (mEq/L)	< 90, > 115	1 / mmol/L	< 90, > 115
Blood Urea Nitrogen (mg/dL)	≥ 30	0.357 / mmol/L	> 10.7
Glucose (fasting) (mg/dL)	≤ 45, ≥ 126	0.05551 / mmol/L	≤ 2.5, ≥11.1
Glucose (random) (mg/dL)	≤ 45, > 200	0.05551 / mmol/L	≤ 2.5, ≥11.1
Lipid Panel (Fasting)			
Total Cholesterol (mg/dL)	≥ 240	0.0259 / mmol/L	≥ 6.2
Triglycerides (mg/dL)	Female: ≥ 170, Male: ≥ 200	0.0113 / mmol/L	Female: ≥ 1.92, Male: ≥ 2.26
HDL-C (mg/dL)	≤ 30	0.0259 / mmol/L	≤ 0.77
LDL-C (mg/dL)	≥ 160	0.0259 / mmol/L	≥ 4.14
Urinalysis			
RBC (hpf)	> 15	N/A	> 15
WBC (hpf)	> 15	N/A	> 15
Sex Hormones			

Parameter (Unit)	Markedly Abnormal Range (Conventional Unit)	Conversion Factor (Conventional to SI) / SI unit	SI Unit Markedly Abnormal Range
FSH (mIU/mL)		1 / IU/L	> 4.2, for Females with Tanner Stage = 1
FSH (mIU/mL)		1 / IU/L	> 10.8, for Females with Tanner Stage = 2
FSH (mIU/mL)		1 / IU/L	> 12.8, for Females with Tanner Stage = 3
FSH (mIU/mL)		1 / IU/L	> 11.7, for Females with Tanner Stage = 4
FSH (mIU/mL)		1 / IU/L	> 9.2, for Females with Tanner Stage = 5
LH (mIU/mL)		1 / IU/L	> 0.18, for Females with Tanner Stage = 1
LH (mIU/mL)		1 / IU/L	> 4.7, for Females with Tanner Stage = 2
LH (mIU/mL)		1 / IU/L	> 12.0, for Females with Tanner Stage = 3
LH (mIU/mL)		1 / IU/L	> 11.7, for Females with Tanner Stage = 4
LH (mIU/mL)		1 / IU/L	> 11.7, for Females with Tanner Stage = 5

Listings will be provided for pregnancy tests. No other summarizations of pregnancy tests will be provided.

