12.4. URINE DRUG SCREENING

Urine drug screening tests are collected at Open-Label Baseline, Week 2, Week 6, Week 10, Week 14, Week 18, Week 22, Week 26, and at the EOS. The urine drug screening data will be presented in a data listing.

12.5. 12-LEAD ECG

Assessment of Standard 12-lead ECG are obtained at each clinic assessment during the study. A central ECG Standard 12-lead ECG will record heart rate (HR), PR interval, RR interval, QT interval, Bazett's corrected QT (QTcB), Fridericia's corrected QT interval (QTcF), and QRS duration. The overall ECG assessment will be centrally reported as "Normal", "Abnormal, Not Clinically Significant", or "Abnormal, Clinically Significant" with respect to relevant abnormalities.

Observed results of each ECG parameter, change from DB baseline, and change from OL baseline will be summarized by DB treatment and overall, and by visit using descriptive statistics.

The QTcF and QTcB results will be adjusted as follows:

$$QTcF = QT / \sqrt[3]{RR}$$

$$QTcB = QT / \sqrt[2]{RR}$$

Bazett's and Fridericia's corrected QT_c values will be classified as having QT_c prolongation according to the following conditions.

QTc Prolongation
QTc >460 msec

QTc Prolongation
Increase from double-blind baseline QTc \geq 60 msec
Increase from double-blind baseline QTc \geq 30 msec
Increase from open-label baseline QTc \geq 60 msec
Increase from open-label baseline QTc \geq 30 msec

The number and percentage of subjects with QTc prolongation using either of the two correction methods (Bazett's, Fridericia's) will be summarized by DB treatment and overall, and by visit.

A shift table comparing the overall ECG assessment from baseline to Week 26 or ET, and from baseline to EOS will be presented.

In addition, the markedly abnormal post-baseline ECG results will also be summarized for subjects with at least one markedly abnormal value during the treatment period. The summary will be completed by DB treatment and overall, and age groups (6 - < 8 years, 8 - < 12 years, 12 - < 16 years, and > 16 years), and overall using the age at the time of the individual assessment.

A listing of markedly abnormal values will be provided.

Criteria for markedly abnormal values, used in the SEP360-202 study, are presented in the table below. They will also be used for the SEP360-310 study summary.

ECG parameter (unit)	Age (years old)	Abnormally Low	Abnormally High
HR (bpm)	6 to <8	< 65	> 115
	8 to <12	< 55	> 110
	12 to <16	< 50	> 105
	\geq 16	< 50	> 100

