12.8. VITAL SIGNS

Vital signs (blood pressure, pulse rate, height, height WHO z-score, weight, BMI, BMI z-score, respiratory rate, and oral temperature) will be monitored at every clinic visit. Respiratory rate and oral temperature will be measured following 5 minutes of supine rest.

At any clinic assessment, orthostatic hypotension (determined by blood pressure measurements only) is defined as having either a ≥ 20 mmHg reduction from supine to standing position in systolic blood pressure (SBP) or ≥ 10 mmHg reduction from supine to standing position in diastolic blood pressure (DBP) or both. Orthostatic tachycardia is defined as heart rate increase ≥ 20 bpm from supine to standing position.

Observed values, change from DB baseline, percent change from DB baseline, change from OL baseline, percent change from OL baseline for each vital sign parameter. will be summarized at each visit by DB treatment and overall.

In addition, the markedly abnormal post-baseline vital signs results will also be summarized for subjects with at least one markedly abnormal value during the treatment period. A listing will be provided for all markedly abnormal vital signs. A shift table will be presented comparing shifts from the baseline visit to Week 26 LOCF. Percentages will be based on the number of safety subjects with a non-missing value for both the baseline and post-baseline visit for the given vital sign. A shift table for BMI classification will also be presented comparing shifts from the baseline visit to Week 26 LOCF.

Parameter (unit)	Age (years old)	Markedly Low	Markedly High
SBP (supine, standing) (mmHg)	6-12	Value ≤ 70 and ≥ 20 decrease from baseline	Value ≥ 120 and ≥ 20 increase from baseline
	13-18	Value ≤ 90 and ≥ 20 decrease from baseline	Value ≥ 135 and ≥ 20 increase from baseline
DBP (supine, standing) (mmHg)	6-12	Value ≤ 40 and ≥ 15 decrease from baseline	Value ≥ 80 and ≥ 15 increase from baseline
	13-18	Value ≤ 50 and ≥ 15 decrease from baseline	Value ≥ 90 and ≥ 15 increase from baseline
Pulse rate (supine, standing) (bpm)	6-10	Value ≤ 60 and ≥ 15 decrease from baseline	Value ≥ 135 and ≥ 15 increase from baseline
	11-18	Value ≤ 50 and ≥ 15 decrease from baseline	Value ≥ 120 and ≥ 15 increase from baseline
SBP orthostatic criteria (mmHg)	~	≥ 20 decrease from supine to standing position	NA
DBP orthostatic criteria (mmHg)	~	≥ 10 decrease from supine to standing position	NA

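### Markedly abnormal laboratory, ECG and orthostatic counts carry no baseline condition, so persistent pre-drug abnormalities are counted together with new ones

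*SAP*

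**What the plan says.** For laboratory tests, SAP 12.2 says that "the markedly abnormal post-baseline laboratory results will be summarized for certain laboratory tests" and then sets the counting rule: "Summaries will be presented separately for hematology and chemistry for subjects with at least one markedly abnormal value during the open-label treatment period". The criteria table that follows uses fixed values or multiples of the normal limits. None of its rows refers to the subject's own baseline.

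For ECG, SAP 12.5 says that "the markedly abnormal post-baseline ECG results will also be summarized for subjects with at least one markedly abnormal value during the treatment period". The HR, PR and QRS limits are absolute and age-specific, and are taken over from the core study.

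For orthostatic findings, SAP 12.8 compares supine with standing at a single visit, for example: "Orthostatic tachycardia is defined as heart rate increase ≥ 20 bpm from supine to standing position".

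The same vital-sign table treats other parameters differently. High systolic pressure at ages 6-12 requires "Value ≥ 120 and ≥ 20 increase from baseline", and the diastolic, pulse and temperature rows likewise combine a limit with a change. SAP 12.5 also has QTc rows for increases of at least 30 and 60 msec from each baseline.

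SAP 6.2.1 defines the DB baseline as the last value up to the first dose in the core study, and the OL baseline as Week 6 (LOCF) of the core study.

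**The concern.** A count of subjects with at least one markedly abnormal value on treatment will usually be read as a statement about what happened on drug. In a controlled trial, pre-existing abnormalities would appear in both arms and could be subtracted. Protocol section 15 describes this study as single-arm with no inference, so nothing here supplies that background.

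The word post-baseline restricts when the value was taken. It says nothing about whether the subject already met the criterion. Entry does not settle this either: exclusion criterion 3 (Protocol 8.2) rests on the judgement of the investigator and medical monitor, not on these limits.

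At stake is the interpretation of secondary safety tables. Laboratory, ECG and vital-sign safety is a stated secondary objective (Protocol 5.2). No hypothesis test is affected.

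**Working it through.** **Criteria side by side**

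| Measure | SAP section | Limit | Change from baseline required? |
|---|---|---|---|
| Laboratory tests | 12.2 | Fixed value or multiple of normal limit | No |
| ECG HR, PR, QRS | 12.5 | Absolute, by age | No |
| Orthostatic SBP, DBP, pulse | 12.8 | Supine-to-standing change within a visit | No |
| SBP, DBP, pulse, temperature | 12.8 | Absolute | Yes |
| QTc increase | 12.5 | At least 30 or 60 msec | Yes, from DB and from OL baseline |

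Heart rate gives the clearest contrast. A high vital-sign pulse needs a rise of at least 15 bpm from baseline; a high ECG heart rate at the same clinic visit does not.

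**Size for persistent abnormalities.** The plan gives no figure to reproduce; 330 is a roll-over projection (SAP 4.2).

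Inputs:
- N = 330, from SAP 4.2, taking every subject to have a post-baseline value.
- b = baseline prevalence of a persistent abnormality that is seen again on treatment (assumed).
- t = true new-onset rate in subjects without it (assumed).

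Formulas:
- Planned count = N[b + (1 − b)t].
- Baseline-negative count = N(1 − b)t, on a denominator of N(1 − b).
- Difference in counts = Nb.

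With t = 0, the planned count is Nb and the baseline-negative count is 0:
- b = 0.5%: 330 × 0.005 = 1.65, about 1.7 subjects
- b = 1%: 3.3
- b = 2%: 6.6
- b = 5%: 16.5

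With t = 1%:

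| b | Planned | Baseline-negative |
|---|---|---|
| 0.5% | 4.9/330 (1.50%) | 3.3/328.4 (1.00%) |
| 1% | 6.6/330 (1.99%) | 3.3/326.7 (1.00%) |
| 2% | 9.8/330 (2.98%) | 3.2/323.4 (1.00%) |
| 5% | 19.6/330 (5.95%) | 3.1/313.5 (1.00%) |

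**Sporadic abnormalities.** Let p be an assumed background probability per visit, independent across visits, with no drug effect, and let k be the number of scheduled on-treatment assessments. The planned count is N[1 − (1 − p)^k]. The baseline-negative count is N(1 − p)[1 − (1 − p)^k] on N(1 − p), which is the same rate. With p = 1%:
- Laboratory tests, k = 2 (Week 14 and Week 26/ET): 330 × 0.0199 = 6.6, against 326.7 × 0.0199 = 6.5.
- ECG and vital signs, k = 9 (Weeks 1, 2, 4, 6, 10, 14, 18, 22, 26): 330 × 0.08648 = 28.5, against 326.7 × 0.08648 = 28.3.

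A baseline condition therefore separates persistent from new abnormalities but does almost nothing for sporadic ones. Those need a per-visit display.

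**What the other outputs cover.** Laboratory shift tables use normal-range categories and end at Week 26 LOCF, so they do not separate new from pre-existing markedly abnormal values. The ECG shift table covers only the overall assessment. No shift is described for the HR, PR or QRS limits or for orthostatic status. Listings show individuals, not rates.

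**The case against.** The plan does not call these values treatment-emergent. It describes them as post-baseline values in the treatment period, which is accurate. Emergence is addressed elsewhere: change from both baselines by visit for laboratory, ECG and vital-sign data; shift tables; QTc-increase rows; listings; and the recording of clinically significant findings as AEs (Protocol 12.2). Protocol 15.3.6.4 already promises orthostatic hypotension at each time point, and SAP 6.1 provides for by-visit summaries that include both baselines. The table shells in SAP Attachment 1 were not available and might contain a baseline split. Removing baseline-positive subjects could also hide worsening in a child who was already abnormal.

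Most of this stands as mitigation, and the last point governs the form of the fix. It does not close the gap, because no described output gives a rate of new markedly abnormal values on these limits. Neither by-visit provision expressly covers orthostatic tachycardia.

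A reader might go further and infer that abnormal baseline values are themselves counted. They are not; the abnormality must be observed again after baseline. A reader might also size the problem by repeated looks: with independent visits, 1 − 0.95^9 = 37% and 1 − 0.90^9 = 61%. Those figures do not measure a missing baseline condition, since the rate is unchanged after conditioning. Nor do they fit the laboratory tests, whose two scheduled draws give 1 − 0.95^2 = 9.8% and 1 − 0.90^2 = 19%.

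**Conclusion.** The point holds as an inexpensive improvement to descriptive safety tables. The laboratory, ECG HR/PR/QRS and orthostatic criteria lack the baseline condition that the SAP applies to blood pressure, pulse, temperature and QTc increase, and the planned counts therefore combine new with persistent pre-drug abnormalities. The excess is Nb: about 1.7 to 16.5 of 330 subjects for b from 0.5% to 5%. This range rests entirely on assumed prevalences, on the full 330 being enrolled and assessed, and on each persistent abnormality being seen again on treatment.

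It would be too strong to conclude that the plan cannot show whether abnormalities emerged on drug. The change-from-baseline summaries, shift tables and listings carry part of that information.

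**What to change.** In SAP 12.2, 12.5 and 12.8, keep the planned all-subject count and add beside it:

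- A treatment-emergent count. Numerator: subjects meeting the criterion on treatment but not at DB baseline. Denominator: subjects not meeting it at DB baseline who have a post-baseline value.
- Columns for prevalence at DB baseline and at OL baseline.
- Per-visit prevalence for the ECG HR/PR/QRS and orthostatic criteria, including orthostatic tachycardia.

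DB baseline is the suitable reference because OL baseline is already on drug for subjects who received dasotraline in the core study. Where DB-baseline status cannot be derived, use OL baseline and say so. The FSH and LH limits are an example: they depend on Tanner stage, and SAP 12.11 names its collection only at OL baseline and Week 26/ET.

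The cost is one or two sentences per section, a filter and a few extra columns. Change from DB baseline is already planned for laboratory, ECG and vital-sign data, so no new data collection is needed for most criteria. The drawback is somewhat smaller denominators in the added column. Keeping the all-subject count ensures that subjects who were abnormal at baseline and worsened stay visible.
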